6. RESPONSE ASSESSMENTS

6.1. Radiographic Evaluations and Confirmation of Disease Progression

Response and progression will be determined by investigator assessment of on-trial radiographic evaluations, that will be conducted every 8 (± 1) weeks through Week 48 and then at least every 12 (± 1) weeks until confirmed progression of disease (as defined below), alternate anticancer therapy, withdrawal of consent, or death, whichever occurs first. The radiographic assessments are to be conducted as noted, independent of dose delays and/or dose interruptions. RECIST 1.1 criteria will be used for primary endpoint evaluation (Eisenhauer et al., 2009), iRECIST will be used for exploratory endpoint response evaluation (Seymour et al., 2017).

Radiographic evaluation may be done using either CT or MRI, but the modality chosen to evaluate each individual subject should be the same as the screening evaluation throughout the duration of the study.

Under specific circumstances subjects who develop PD per RECIST v1.1 may continue treatment and be followed for improved response or confirmed progression of disease [treatment beyond progression (Section 6.2)]. Regardless of whether or not a subject continues treatment in the event of RECIST-determined PD, follow-up radiographic assessments to confirm progression or show improvement in response are to be conducted at least 4 weeks after the assessment of PD per RECIST v1.1 (unless there is prior clinical deterioration, initiation of other cancer therapy, or withdrawal of consent).

For subjects who continue treatment beyond progression (Section 6.2), iRECIST PD should be confirmed at least 4 to 8 weeks after the first radiologic evidence of PD in clinically stable participants.

Subjects who have unconfirmed PD (iUPD) may continue study treatment until progression is confirmed as long as the subject is clinically stable and has provided written informed consent prior to receiving additional treatment (Section 6.2). Clinically unstable subjects should be discontinued from study treatment at the first occurrence of radiographic PD (iUPD) and are not required to have repeat imaging to confirm PD by iRECIST (though a confirmation of progression scan may be obtained at the investigator's discretion after consultation with the sponsor).

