If repeat imaging shows iRECIST confirmed disease progression (iCPD), subjects will discontinue treatment. However, if the subject is deriving benefit after iCPD is observed, an exception to continue study treatment must be approved by the sponsor's Medical Monitor. Subjects who have repeat imaging to confirm progression are not required to undergo the next scheduled tumor imaging if it is less than 4 weeks later.

If repeat imaging shows iRECIST stable disease (iSD), iRECIST partial response (iPR), or iRECIST complete response (iCR), imaging should be continued every 8 (± 1) weeks and the subject should continue on trial treatment.

Note that the date of progression to be used for all relevant efficacy endpoints will be based on first documentation of PD (ie, RECIST v1.1 date of PD), regardless of date of confirmation of PD for subjects who continue on treatment.

All radiographic evaluations performed on the study will be collected and held for a potential independent review. Details regarding initiating an independent review will be outlined in the statistical analysis plan (SAP).

Confirmed progression of disease is defined as one of the following:

Clinical deterioration with or without radiographic PD per RECIST v1.1 (See [Appendix 7](#)) will confirm progression of disease. Note, however, that radiographic evaluation should be conducted at the time of clinical signs and/or symptoms of PD whenever possible.

- In subjects without clinical deterioration at the time of a radiographic scan showing PD per RECIST v1.1, a second scan conducted at least 4 weeks later showing progression of disease as outlined below will confirm progression:
- An additional 10% increase in tumor burden with a minimum 5 mm absolute increase from time of initial PD. This includes an increase in the sum of diameters of all target lesions and/ or the diameters of new measurable lesions compared to the time of initial PD.

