10.8.3. Exploratory Endpoints

10.8.3.1. Objective Response Rate (iRECIST)

The same target and non-target lesions will be used to assess response as per the iRECIST criteria.

One key difference for iRECIST as compared to RECIST v1.1 is that PD has to be confirmed. As per iRECIST, the appearance of new lesions will result in immune unconfirmed progressive disease (iUPD), with immune confirmed progressive disease (iCPD) being assigned if additional new lesions appear or new lesions increase in size (≥ 5 mm for sum of new target lesions or any increase in new non-target lesions).

iCR, iPR, iSD are defined as per Table 6, with the main difference from the assignments per RECIST v1.1 being that a subject can experience iUPD prior to iCR, iPR, iSD but not iCPD, i.e. they can have progression recorded at a visit but it needs to be confirmed at the subsequent visit for the overall response to be iCPD.

Table 6: Some Examples for Assigning Timepoint Response for iRECIST

		Time Point Response		
Target lesions	Non-Target lesions	New Lesions	No Prior iUPD	Prior iUPD
iCR	iCR	No	iCR	iCR
iCR	Non-iCR/Non-iUPD	No	iPR	iPR
iPR	Non-iCR/Non-iUPD	No	iPR	iPR
iSD	Non-iCR/Non-iUPD	No	iSD	iSD
iUPD with no change OR decrease from last TP	iUPD with no change OR decrease from last TP	Yes	NA	NLs confirms iCPD if NLs were previously identified and increase in size (≥ 5 mm in SOM for NLT or any increase for NLNT) or number; If no change in NLs (size or number) from last TP, remains iUPD
iSD, iPR, iCR	iUPD	No	iUPD	Remains iUPD unless iCPD confirmed based in further increase in size of NT disease (need not meet RECIST v1.1 criteria for unequivocal PD)
iUPD	Non-iCR/Non-iUPD ; iCR	No	iUPD	Remains iUPD unless iCPD confirmed based on: further increase in SOM of at least 5 mm, otherwise remains iUPD
iUPD	iUPD	No	iUPD	Remains iUPD unless iCPD confirmed based on further increase in: 
 previously identified T lesion iUPD in SOM ≥ 5 mm and / or NT lesion iUPD (prior assessment – need not be unequivocal)
iUPD	iUPD	Yes	iUPD	Remains iUPD unless iCPD confirmed based on further increase in 
 previously identified T lesion iUPD SOM ≥ 5 mm and / or previously identified NT lesion iUPD (need not be unequivocal) and /or size or number of new lesions previously identified
Non-iUPD/PD	Non-iUPD/PD	Yes	iUPD	Remains iUPD unless iCPD confirmed based on increase in size or number of new lesions previously identified

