10.8.3.2. Duration of Response (iRECIST)

Duration of response (DoR) is defined as the time, in days, from the first of the 2 assessments required for confirmed iPR or iCR to the time of the iCPD or death due to underlying cancer.

The duration will be calculated (in days) as:

Date of first overall response of iCPD or date of death due to underlying cancer (whichever is first) – Date of first of the two assessments required for confirmed iCR or iPR.

The duration of response will be summarised by cohort using descriptive summaries, which will not account for censoring. Additionally, Kaplan-Meier curves will be produced for each cohort along with a table summarising the median and 25th and 75th percentiles of the duration of response, inclusive of censoring, for each cohort, including sub-cohort.

[Kaplan-Meier plot: y-axis = cumulative proportion of participants who still have response, x-axis = day, one line for each cohort, including sub-cohort, overlayed on the same plot].

Exclusion

If a subject does not achieve confirmed iCR or iPR they will be excluded from this analysis.

Censoring

If a subject does not experience iCPD or death due to underlying cancer their duration will be censored at the date of their last disease assessment.

If a subject dies due to a cause other than underlying cancer they will be censored at the date of death.

If a subject does not have a disease assessment after their assessment confirming their response as iCR or iPR they will be censored at the date of their last disease assessment.

If a subject initiates another cancer treatment prior to iCPD/death their duration of response will be censored at the last assessment prior to initiation of the alternative cancer treatment.

If a subject experiences iCPD or death immediately following 2 or more visits at which their response was missing or NE their duration of response will be censored at the time of their last assessment prior to missing/NE response.

10.8.3.3. *Progression Free Survival (RECIST)*

Progression-free survival (PFS) is defined as the time, in days, from the first date of treatment until the first date at which PD is experienced or the subject dies due to any cause. Only deaths that occur within 30 days of the last tumor assessment will be included.

The duration will be calculated (in days) as:

Date of first overall response of PD or date of death due to any cause (whichever is first) – Date of first treatment.

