Progression-free survival will be summarised by cohort, and sub-cohort for cohort F, using descriptive summaries, which will not account for censoring. Additionally, Kaplan-Meier curves will be produced for each cohort, and sub-cohort for cohort F, along with a table summarising the median and 25th and 75th percentiles of the progression-free survival, inclusive of censoring, for each cohort, including sub-cohort.

[Kaplan-Meier plot: y-axis = cumulative proportion of participants who are progression free, x-axis = day, one line for each cohort, including sub-cohort, overlayed on the same plot].

Censoring

If a subject does not experience PD or death they will be censored at the date of their last disease assessment.

If a subject does not have a disease assessment after their first treatment they will be censored at the date of their first treatment.

If a subject initiates another cancer treatment prior to PD/death they will be censored at the last assessment prior to initiation of the alternative cancer treatment.

If a subject experiences PD or death immediately following 2 or more visits at which their response was missing or NE they will be censored at the time of their last assessment prior to missing/NE response.

10.8.3.4. *Progression Free Survival (iRECIST)*

Progression-free survival (iPFS) is defined as the time, in days, from the first date of treatment until the first date at which iCPD is experienced or the subject dies due to any cause. Only deaths that occur within 30 days of the last tumor assessment will be included.

The duration will be calculated (in days) as:

Date of first overall response of iCPD or date of death due to any cause (whichever is first) – Date of first treatment.

Progression-free survival will be summarised by cohort, and sub-cohort for cohort F, using descriptive summaries, which will not account for censoring. Additionally, Kaplan-Meier curves will be produced for each cohort, and sub-cohort for cohort F, along with a table summarising the median and 25th and 75th percentiles of the progression-free survival, inclusive of censoring, for each cohort, including sub-cohort.

[Kaplan-Meier plot: y-axis = cumulative proportion of participants who are progression free, x-axis = day, one line for each cohort, including sub-cohort, overlayed on the same plot].

Censoring

If a subject does not experience iCPD or death they will be censored at the date of their last disease assessment.

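### The SAP dates iRECIST progression at the confirming scan, contrary to the protocol's first-documentation rule and undeclared, which lengthens iPFS and usually iRECIST duration of response by at least about 28 days

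*SAP*

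**What the plan says.** **SAP, end dates.** For iPFS (10.8.3.4) the end date is the "Date of first overall response of iCPD or date of death due to any cause (whichever is first", less the date of first treatment. For iRECIST DoR (10.8.3.2) it is the "Date of first overall response of iCPD or date of death due to underlying cancer (whichever is first", less the date of the first of the two response assessments.

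**SAP, when iCPD arises.** Section 10.8.3.1 explains that progression may be recorded at a visit, but "it needs to be confirmed at the subsequent visit for the overall response to be iCPD". The date of first iCPD is therefore the date of the confirming scan.

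**Protocol 6.1, dating rule.** After the paragraphs on confirming progression under iRECIST, the protocol adds a note on dating, which reads in part "progression to be used for all relevant efficacy endpoints will be based on first documentation of PD (ie, RECIST v1.1 date of PD"). It adds that this holds "regardless of date of confirmation of PD for subjects who continue on treatment".

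**Protocol 6.1, confirmation interval.** Repeat imaging comes no sooner than 4 weeks after RECIST v1.1 progression. For treatment beyond progression, "iRECIST PD should be confirmed at least 4 to 8 weeks after the first radiologic evidence of PD in clinically stable participants".

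**Protocol 9.3.1.** iRECIST endpoints are to be analysed by the same statistical method as their RECIST 1.1 counterparts.

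**SAP Sections 4 and 11.** Section 4 promises that departures from the protocol's analyses will appear in Section 11. That section lists an added definition of treatment-emergent adverse event and the decision not to summarise laboratory toxicity grades. It says nothing about the progression date.

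**The concern.** RECIST v1.1 PFS (SAP 10.8.3.3) stops at the first progression. iPFS stops at the scan that confirms it. Both are estimated in the same response-evaluable subjects and reported in matching tables (14.2.7 and 14.2.8) and Kaplan-Meier figures (14.2.3.4 and 14.2.3.5).

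Take a subject whose progression is simply confirmed at the next scan, with no pseudoprogression. That subject gets a longer iPFS than PFS, although nothing about the disease course differs between the two criteria. The shift always goes the same way, and a reader comparing the curves could take the gap for delayed immune benefit. The change from the protocol's rule is also missing from the section meant to record such changes.

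**Working it through.** **Inputs**
- End of iPFS and iRECIST DoR: first iCPD (SAP 10.8.3.4 and 10.8.3.2).
- End of RECIST v1.1 PFS: first PD (SAP 10.8.3.3).
- Confirmation: at least 4 weeks, or at least 4 to 8 weeks for treatment beyond progression (protocol 6.1).
- Routine scans: every 8 (±1) weeks through Week 48, then at least every 12 (±1) weeks (protocol 6.1).
- iUPD can persist over further scans if nothing changes, and can precede an iRECIST response (protocol Appendix 7).

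**The plan's own figure.** The only stated interval is the confirmation window: 4 × 7 = 28 days and 8 × 7 = 56 days. The wording sets a minimum and gives no maximum, so 28 days is a floor and 56 days is not a ceiling.

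**Formula.** Excess = date of first iCPD − date of first documented PD.

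If the ± week is read as applying to the gap between successive scans, confirmation at the next routine scan gives:
- through Week 48: 7 × 7 = 49 to 9 × 7 = 63 days;
- after Week 48: up to 13 × 7 = 91 days.

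**Constructed subjects** (first treatment on Day 1; the SAP subtracts dates without adding 1):

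| Scan sequence | RECIST v1.1 PFS | iPFS per SAP | Excess |
|---|---|---|---|
| PD Day 57, confirmed Day 85 | 56 | 84 | 28 days |
| PD Day 57, confirmed Day 113 | 56 | 112 | 56 days |
| iUPD Day 57, unchanged Day 113, iCPD Day 169 | 56 | 168 | 112 days (16 weeks) |
| PD Day 337, confirmed 13 weeks later (Day 428) | 336 | 427 | 91 days |

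**Duration of response, ordinary case.** Response first seen Day 113 and confirmed Day 169; progression first seen Day 225 and confirmed Day 281.
- SAP iRECIST DoR: 281 − 113 = 168 days.
- Dated at first progression: 225 − 113 = 112 days.
- Excess: 56 days.

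**Duration of response, pseudoprogression.** Same subject, with an earlier iUPD on Day 57 before the response.
- Literal first PD: 57 − 113 = −56 days, which is impossible. Protocol 6.1 cannot be applied word for word to this endpoint.
- First iUPD of the confirmed episode: 225 − 113 = 112 days.
- For iPFS, the SAP gives 281 − 1 = 280 days and confirmed-episode dating gives 225 − 1 = 224. RECIST v1.1 PFS is 57 − 1 = 56.
- Of the 280 − 56 = 224-day difference, 224 − 56 = 168 days reflect a real difference between the criteria. The other 280 − 224 = 56 days are dating alone. The SAP's rule mixes the two.

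**What is not touched.** The Simon designs rest on objective response. P(reject) = Σ P[Bin(10, p) = x] × P[Bin(19, p) ≥ c − x], summed from x = 1 with c = 4 for Type 1 and from x = 2 with c = 6 for Type 2. This reproduces the plan: 0.0468 and 80.11% for Type 1 (p = 0.05, 0.2), and 0.0471 and 80.51% for Type 2 (p = 0.1, 0.3). No progression date enters.

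**The case against.** The best counter-argument is that protocol 6.1 never meant to govern iRECIST endpoints. It says *relevant* endpoints and ties the date to RECIST v1.1. Applied literally, it would give progression the same date under both criteria. Yet the protocol lists PFS under each as separate measures, and its iRECIST table requires progression to be confirmed. Protocol 9.3.1 cuts both ways, because the SAP does use a parallel formula with iCPD in place of PD.

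Part of this stands. A reader might infer that protocol 6.1 fixes the first PD date for every efficacy endpoint without exception; the text does not go that far. Nor does it contain the reset rule that a workable iRECIST derivation needs.

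The narrow reading is still the weaker one. The note directly follows the iRECIST confirmation paragraphs and is written for subjects who stay on treatment past progression, for whom the first and confirming dates differ. Even on the narrow reading, the protocol would leave the iRECIST event date unstated, and the SAP should settle it openly.

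It is also fair that the endpoints are exploratory, that no formal testing is planned (SAP 10.1.3), that the study was terminated (SAP 6.3), and that visit-level iRECIST responses are listed with dates (Listing 16.2.6.3.2), so a careful reader could recover the gap. That limits the consequence. It does not remove the conflict or the missing declaration.

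**Conclusion.** The point holds in a bounded form. SAP 10.8.3.2 and 10.8.3.4 date iRECIST progression at the confirming scan, which conflicts with protocol 6.1 and is not declared in SAP Section 11. For scan-confirmed progression, iPFS and usually iRECIST DoR run longer by at least about 28 days. The gap is about 49 to 63 days with confirmation at the next routine scan through Week 48, up to about 91 days after that, and more if iUPD persists. These figures assume that scans follow the protocol's windows.

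Two stronger readings are tempting and not supported:
- **That durations are 4 to 8 weeks too long.** The protocol states a minimum interval, not a range.
- **That the shift can be set against the 57.5-day median PFS of the earlier combination study.** That compares one subject's date change with a Kaplan-Meier median from a 10-subject group (95% CI 14.0 to 224.0 days). The cohort median need not move by the individual shift, because deaths are not shifted and clinically unstable subjects need no confirming scan.

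Objective response rate, RECIST v1.1 DoR and RECIST v1.1 PFS are unaffected. Subjects with iUPD who never have a confirming scan raise a separate question that is not covered here.

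**What to change.** In SAP 10.8.3.2 and 10.8.3.4, keep iCPD as the requirement for a progression event, but date the event at the first iUPD of the episode that iCPD later confirms. State that an iUPD followed by iSD, iPR or iCR closes that episode and does not supply the event date.

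In Section 11, record the rule and its relation to protocol 6.1. It applies the protocol's first-documentation principle. The reset is an added clarification, needed because a literal first PD date can precede an iRECIST response. If the sponsor prefers to date at confirmation, Section 11 should declare that, and the iPFS and iRECIST DoR outputs should carry a footnote saying so.

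The cost is a sentence or two in each of two sections, an entry in Section 11, and a date derivation from time-point responses already collected. No new data are needed. The iRECIST durations become slightly less favourable.

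### Exploratory iPFS censors subjects stopped for clinical deterioration at an unconfirmed progression with no later evaluable scan; a sensitivity analysis should show how much this matters

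*SAP*

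**What the plan says.** **SAP.** Section 10.8.3.4 defines the iPFS event as iCPD or death from any cause, with a limit on deaths: "Only deaths that occur within 30 days of the last tumor assessment will be included". A subject with neither is handled thus: "If a subject does not experience iCPD or death they will be censored at the date of their last disease assessment". New cancer treatment before iCPD or death censors at the last assessment before that treatment. Section 10.8.3.1 requires progression to be confirmed at the following visit before it becomes iCPD, and gives no route through clinical deterioration.

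**Protocol 6.1.** The rule for those who are not stable reads: "Clinically unstable subjects should be discontinued from study treatment at the first occurrence of radiographic PD (iUPD) and are not required to have repeat imaging". At the investigator's discretion, and after consulting the sponsor, "a confirmation of progression scan may be obtained". The general follow-up scan at least 4 weeks after RECIST progression is required "unless there is prior clinical deterioration, initiation of other cancer therapy, or withdrawal of consent". The section also lists what confirms progression of disease, and the first entry is "Clinical deterioration with or without radiographic PD per RECIST v1.1". Scheduled imaging runs "until confirmed progression of disease (as defined below), alternate anticancer therapy, withdrawal of consent, or death, whichever occurs first".

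**The concern.** The protocol waives the only imaging evidence that the SAP accepts, and it does so for subjects who are progressing and clinically worse. They leave the iPFS risk set on the day progression is seen, for a reason tied to their prognosis. Kaplan-Meier estimation assumes that censored subjects have the same outlook as those who stay at risk. Here they do not, and the bias runs upward.

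iPFS is reported beside RECIST PFS, so a reader will compare Table 14.2.7 with Table 14.2.8. The gap should show iUPD that later reversed. Under the current rule it also contains deterioration stops that were merely censored, and the two tables alone do not separate them.

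**Working it through.** The plan states no iPFS figure, so there is none to reproduce. The check is a trace of the rules, followed by an illustration of size.

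**1. One subject through the rules.** iUPD is seen on day X, the subject is clinically unstable, treatment stops, and there is no later evaluable scan.
- Protocol 6.1: no repeat scan is required, and progression counts as confirmed for stopping treatment and imaging.
- Protocol Appendix 7 (iRECIST best overall response): iUPD followed only by non-evaluable visits stays iUPD.
- SAP 10.8.3.4, subject alive or dying after day X+30: not an event. The SAP has no explicit rule for the late death; censoring at the last assessment is the natural reading.
- SAP 10.8.3.4, death by day X+30 with no new therapy: event at death.
- SAP 10.8.3.4, new therapy before death: censored at the last assessment before it.
- SAP 10.8.3.3 (RECIST PFS): the same scan is an event on day X, subject to that section's own censoring rules.
- SAP 10.8.3.2 (iRECIST duration of response): a later death from the underlying cancer counts with no 30-day limit, unless new therapy starts first. The gap is smaller there.

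**2. Size in a single-scan model.** Inputs: s, the share free of progression; q, the share of first progressors who take this path (assumed; no document gives it). All other progressors are confirmed 4 weeks after iUPD. As a scale for s, Protocol 1.2 gives a 3-month PFS of 37.5% (95% CI 8.7 to 67.4) for the earlier combination group.
- At risk at the confirming scan: 1 − (1−s)q. Still free: s.
- iPFS under the current rule: s / (1 − (1−s)q).
- Counted as events at iUPD: (1 − (1−s)q) × s / (1 − (1−s)q) = s.

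| s | q | Current rule |
|---|---|---|
| 37.5% | 10% | 0.375/0.9375 = 40.0% |
| 37.5% | 20% | 0.375/0.875 = 42.9% |
| 37.5% | 40% | 0.375/0.75 = 50.0% |
| 37.5% | 60% | 0.375/0.625 = 60.0% |
| 8.7% | 20% | 0.087/0.8174 = 10.6% |
| 67.4% | 20% | 0.674/0.9348 = 72.1% |

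In a 10-subject cohort with 6 first progressions at Week 8, censoring k of them gives 4/(10−k) at Week 12. For k = 0 to 4 this is 40.0%, 44.4%, 50.0%, 57.1% and 66.7%, against 40.0% if they are counted.

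**3. Several scans.** Assume exponential progression with median 57.5 days (the earlier combination group's median PFS, Protocol 1.2), scans every 56 days, and iCPD 28 days after iUPD. The shares free of progression at days 56, 112 and 168 are a = 0.5^(56/57.5) = 0.509, b = 0.5^(112/57.5) = 0.259 and c = 0.5^(168/57.5) = 0.132. At day 180 two confirming scans have passed, but three scheduled scans.
- Current rule: [a / (1 − (1−a)q)]².
- Counted as events at iUPD: b − q(b − c).

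| q | Current rule | Counted as events |
|---|---|---|
| 0 | 25.9% | 25.9% |
| 10% | 28.7% | 24.6% |
| 20% | 31.9% | 23.4% |
| 30% | 35.6% | 22.1% |
| 50% | 45.5% | 19.6% |

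A simulation of 200,000 subjects under the same assumptions agrees to within about 0.2 points. The counted estimate drifts below 25.9% because these events are dated at the iUPD scan, while iCPD events wait for confirmation.

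**The case against.** **The SAP applies iRECIST as written.** This stands. A reader might infer that the SAP contradicts the protocol, because Protocol 6.1 calls this case confirmed progression. The documents do not go that far. Section 6.1 uses the label iCPD only for repeat imaging, and its broader definition governs stopping treatment and scans. Appendix 7 uses clinical status to decide on continuing treatment after iUPD, not to assign response. So the current rule can remain the main analysis.

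**A scan may still be done.** Also true. It is allowed at discretion, and Protocol 6.1 asks for imaging at clinical signs of progression whenever possible. That reduces the number affected but does not remove the path.

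**The cases can be identified.** A reader might infer that reversed iUPD and deterioration stops cannot be told apart. In the two summary tables they cannot. In the subject listings they can: Listing 16.2.6.3.2 has iRECIST response by visit, 16.2.6.4.2 has iPFS, and 16.2.1.1 has the reason for stopping. What is missing is a summary.

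**The endpoint is exploratory.** iPFS is exploratory, SAP 10.1.3 plans no hypothesis tests, and RECIST PFS already counts the same first progression. This limits the severity. It does not make the iPFS curve correct.

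**Conclusion.** The gap is real and its direction is known: exploratory iPFS is biased upward, and iRECIST duration of response less so. Its size is unknown, because nothing in the documents gives the number of subjects who take this path. The figures above are illustrations under an assumed q, with confirmation 4 weeks after iUPD. Protocol 6.1 allows 4 to 8 weeks for subjects treated beyond progression. With confirmation only at Week 16, the Week 12 comparison would look quite different.

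A reader might take the single-scan result to mean that counting these subjects always recovers the true value whatever q is. It does so only in that model. With several scans the counted estimate falls somewhat below the fully confirmed value, from 25.9% to 24.6% at q = 10% and to 19.6% at q = 50%. The two analyses therefore sit on either side of the fully confirmed value in this illustration, which is a reason to show both and not to replace one with the other.

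Severity is minor. The primary RECIST v1.1 ORR and RECIST PFS are unaffected. Deterioration with no radiographic progression is a separate matter and is not covered here.

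**What to change.** Keep the current iRECIST rule as the main analysis. Add one sensitivity analysis to SAP 10.8.3.4, and to 10.8.3.2 for subjects with confirmed iCR or iPR:

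*A subject whose last evaluable iRECIST response is iUPD (including iUPD followed only by NE or missing), whose treatment was stopped for clinical deterioration or disease progression, and who would otherwise be censored, is an event at the first assessment of that unresolved iUPD. This takes precedence over new-treatment censoring if the new treatment started after that iUPD. Subjects already counted as events under the main rule keep their event and date.*

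Report the number reclassified per cohort beside Table 14.2.8.

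**Check first:** the recorded reasons for stopping treatment. Protocol 4.2 and Section 7 list progression-type reasons but no separate clinical-deterioration category, and the SAP shells do not show the categories. That is why the wording includes disease progression.

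**Cost:** a short paragraph in two SAP sections and a rerun of Table 14.2.8, Figure 14.2.3.5 and the iRECIST duration-of-response outputs. No protocol change is needed, and no new data collection is expected if the recorded reasons prove usable.

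**Downsides:** some iUPD that might have been pseudoprogression will count as events, and these events are dated earlier than iCPD events. A footnote should state both.
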